required methodological modifications. The safety data will be summarized by treatment group and site. Adverse events will be tabulated. These will include the number of participants for whom the event occurred, the rate of occurrence, and the severity and relationship of adverse events to study treatment. Safety data will be analyzed using ANOVAs for continuous variables and Chi-square analyses for dichotomous variables at each time point. Wilcoxon-Mann-Whitney rank-sum test will be used to analyze treatment arm versus control arm across study visits and sites. We anticipate using non-parametric tests because the majority of the outcome measures used in our research may not be normally distributed. The Kruskal-Wallis test will be used to determine whether samples from each of the two arms originated from the same distribution. Since nonparametric tests are based on complete data and ignore missing follow-up data, general linear mixed regression modeling (Gibbons et al, 1988; Hedeker et al, 199; Laird et al, 1982) will be used to confirm the results of the nonparametric tests. The two arms will be compared over time with a focus on the treatment by Time interaction effect. Mixed regression modeling offers robust handling of missing data (Little, 1996) with an assumption that the data is missing at random. This method allows the inclusion of subjects with missing data or those who were terminated early in the study, without relying on data imputation procedures. This method provides an estimate of the individual variability around the population trend, the variability of the individual intercepts (baseline values) and slopes (changes across time), and the correlation between them. Co-variance structure will be chosen based on Akaike's Information Criterion (AIC). Random group level treatment effects will also be evaluated for importance based on the model AIC. Denominator degrees of freedom will be calculated using the Kenward-Roger small sample correction.

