A detailed list of feasibility outcomes is provided in the previous section. Briefly, feasibility outcomes will be assessed by determining: 1) Numbers of potentially eligible and ineligible patients, number contacted, and consent rates. 2) Feasibility of recruiting sites in which staff are interested in participating in a future main trial. 3) Rate of retention in the trial, including response rates to questionnaires and individual measures. 4) Intervention fidelity and adherence using case report forms and patient-completed personal diaries. 5) Determining the primary outcome measure for the main trial by assessing and comparing sensitivity to change of the measures and other statistical properties, comparing follow-up rates of different methods of data capture and of individual measures, and evaluating which outcome measures best reflect the patients' recovery goals, as identified from the collected data.

As indicated above, the primary aims of our data analytic strategy for sub-studies 1a and 1b will be directed toward examining the safety and feasibility of the treatments. Although it is not our major focus, we also aim to estimate effect sizes to assist in future power calculations. However, recent work by Kraemer (2006) has highlighted important limitations of this aim due to the large standard error surrounding the pilot study effect size. As a result, the primary focus of our analyses will remain on safety and feasibility and we will report our findings with this limitation in mind. Our goal is to collect important data regarding our ability to implement recruitment strategies, and the safety and feasibility of the treatments and measurements. Information derived from this research will lead to better-designed full-scale studies and help inform decisions regarding whether it is worthwhile to commit additional resources to future treatment development. Due to our small sample size, our statistical analytical findings will be interpreted with caution. Sub-study 1c will include sufficient number of subjects to test for treatment efficacy.

Data will be analyzed from all randomized subjects. All statistical tests will be two-tailed. Differences will be considered statistically significant provided a p-value of 0.05 or less is obtained. The significance level for the tests will be adjusted with a Bonferroni correction for multiple comparisons, if needed. Data will be analyzed using SPSS version 27.

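### All randomized participants are to be analysed, yet the arm comparison rests on rank tests the plan says ignore missing follow-up; the planned mixed model should lead, above all in sub-study 1c

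*Combined protocol and SAP*

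**What the plan says.** Everything here is in section 9 of the combined protocol and SAP, mostly under Statistical Methods And Considerations.

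- **Who is analysed:** "Data will be analyzed from all randomized subjects".
- **How the arms are compared:** "Wilcoxon-Mann-Whitney rank-sum test will be used to analyze treatment arm versus control arm across study visits and sites". The reason given is distributional: "We anticipate using non-parametric tests because the majority of the outcome measures used in our research may not be normally distributed".
- **What those tests do with missing data:** "Since nonparametric tests are based on complete data and ignore missing follow-up data, general linear mixed regression modeling" (the sentence continues) "will be used to confirm the results of the nonparametric tests".
- **What the mixed model covers:** "This method allows the inclusion of subjects with missing data or those who were terminated early in the study, without relying on data imputation procedures". Its validity condition is stated: "with an assumption that the data is missing at random".
- **Other tests:** safety data are also to be analysed with ANOVA and chi-square at each time point.
- **Missing-data checks:** missingness is to be examined for randomness, and dropouts are to be compared with completers on baseline data. A lack of significant differences is taken as support for random dropout.

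Dropout is a planning figure. Sample Size Justification anticipates 20%, and the opening design text in section 9 speaks of up to 20%. The plan does not name one primary test, endpoint or visit, does not say whether complete data means complete at the visit tested or at all visits, and gives no rule for a disagreement between the rank tests and the mixed model.

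**The concern.** The analysis that fits the all-randomized statement is placed behind the one that does not. A rank test restricted to people with data compares subsets left after randomization. If leaving the study is related to how a participant feels, those subsets may differ between arms for reasons other than treatment effect.

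That is a realistic possibility here because the likely reasons for leaving are close to the outcomes. In 1c, vaccine side effects and post-peak antibody decline are objectives (section 6) and blood sampling runs to 6 months, where loss may be largest. In 1a and 1b the Day 14 blood draw is for participants who are not hospitalized, while laboratory values for hospitalized participants come from hospital records. A complete-data Day 14 comparison may therefore miss, or measure differently, the sickest participants.

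The plan's check on dropout is weak protection. Baseline data cannot show dropout driven by symptoms that arise later, and with about 6 planned dropouts per arm in 1a and 1b a non-significant comparison says little.

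Without a rule for disagreement, the choice between the two results could be made after they are seen. That matters most in 1c, the sub-study described as large enough to test efficacy.

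**Working it through.** **1. Reproduce the plan's dropout figures (Sample Size Justification).**

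- 1a and 1b: 27 × (1 + 0.20) = 32.4, rounded up to 33 per arm, 66 in total. This matches the plan. The built-in loss is 6/33 = 18.2%.
- 1c: 0.20 × 266 = 53.2, which matches the stated 53 extra participants and gives 266 + 53 = 319. The opening of section 9 and section 10 instead give 266 as the total (133 per arm), so the 1c denominator is unclear.

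**2. Participants left in a complete-data test if the full allowance is lost.**

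- 1a and 1b: 33 − 6 = 27 per arm, the plan's own completer target.
- 1c with 266 enrolled: 133 × 0.80 = 106.4, about 106 per arm (213 in total).
- 1c with 319 enrolled: 319 × 0.80 = 255.2, about 127 per arm.
- With smaller losses in 1c: 5% leaves 253 of 266, 10% leaves 239, and 15% leaves 226.

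A rank test at a single visit omits only those missing at that visit, so early visits may lose fewer. If complete data means complete at every visit, the loss could exceed the dropout rate.

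**3. Power.** Inputs from the plan are two-sided testing, a 0.05 threshold and equal allocation. The plan mentions a medium effect but gives no number, SD or target power, so d = 0.3 to 0.5 is an assumption. Two-sample t-test power (noncentral t, noncentrality d × √(n/2), n per arm) stands in for the rank test.

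| Sub-study | n per arm | d = 0.3 | d = 0.4 | d = 0.5 |
|---|---|---|---|---|
| 1c, all of 266 | 133 | 68.4% | 90.1% | 98.2% |
| 1c, 20% missing from 266 | 106 | 58.5% | 82.6% | 95.2% |
| 1c, 20% missing from 319 | 127 | 66.3% | 88.8% | 97.8% |
| 1a/1b, all | 33 | – | – | 51.6% |
| 1a/1b, completers | 27 | – | – | 43.8% |

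In 1c with 266 enrolled, the gap is 9.9 points at d = 0.3, 7.5 at d = 0.4 and 3.0 at d = 0.5. These gaps are upper bounds on what the mixed model could recover, because a participant who leaves early contributes only part of the information.

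**4. When the loss would cross 80% power in 1c.** By the normal approximation, the effect detectable with 80% power is 2.8016 × √(2/n): 0.344 at n = 133 and 0.385 at n = 106. The loss moves 1c from above to below 80% only if the true d lies in that narrow band.

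**5. Bias.** Its size depends on the dropout mechanism and cannot be computed from the documents.

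**The case against.** The strongest reply is that the plan has largely dealt with this. It discloses the limit of the rank tests, prespecifies a mixed model that keeps early terminators, states the missing-at-random assumption, specifies a Kenward-Roger correction and includes missingness diagnostics. The all-randomized sentence can be read as satisfied by that model. This stands in part: nobody with usable data is left out of the analysis altogether. It does not settle which result counts, and giving the model a confirming role points the wrong way.

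A reader might go further in three ways that the documents do not support.

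- **That the rank tests are the formally designated headline analysis.** No test is designated. Their leading role is an inference from the arm comparison being assigned to them and the model being there to confirm.
- **That about 20% of participants will be missing from the comparison.** The 20% is an allowance, and the loss varies by visit.
- **That the power loss is serious throughout.** In 1c at d = 0.5 it is 3.0 points, and if 319 are enrolled the remaining 127 per arm come close to the planned 133. In 1a and 1b, 27 per arm is the intended completer number, the focus is safety and feasibility, and the plan says its findings there will be interpreted with caution.

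Adverse event tabulations and the recruitment and retention counts are largely unaffected.

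It is also fair to say that the mixed model is not a full cure. If dropout depends on values never observed, the model is biased too. Skewed symptom scores may also not be well described by a linear model, even after transformation.

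**Conclusion.** The point holds as an inconsistency with a missing decision rule: the commitment to analyse everyone randomized is not met by the tests assigned to compare the arms, and the model that can use incomplete follow-up is ranked behind them. It should be corrected, chiefly for 1c.

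Up to about 20% of participants could be absent from late-visit rank tests if the planning allowance is fully used. In 1c the corresponding power cost is at most 3.0 to 9.9 points for d between 0.5 and 0.3 with 266 enrolled. These figures rest on assumed effect sizes and on t-test power as an approximation. At a medium effect of d = 0.5, the main concern in 1c is bias from outcome-related dropout and the open choice between two results, more than lost power. In 1a and 1b the issue is secondary.

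**What to change.** Amend Statistical Methods And Considerations as follows.

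1. For repeated continuous outcomes, above all antibody titre in 1c, make the planned mixed model on all randomized participants the primary analysis, with log transformation where needed (the section already allows for this).
2. Keep the rank tests as a sensitivity analysis, and say whether they use participants complete at the visit tested or at all visits.
3. State that conclusions follow the mixed model if the two disagree.
4. Add a sensitivity analysis for departures from missing at random, since the model does not protect against dropout that depends on unobserved values.
5. Settle whether 1c enrols 266 or 319, so that the all-randomized denominator is defined.

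The cost is SAP wording and a little more analysis work, since the model is already planned and no extra participants or visits are needed. The drawback is reliance on a transformed-scale model for skewed outcomes; the retained rank tests are the check on that.

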#### B. Feasibility:

The following feasibility data will be collected and assessed :

- 1) Recruitment:
  - a. Recruitment sites (number, location, and method of their selection)
  - b. Factors influencing recruitment rate
  - c. Methods used for subject recruitment
  - d. Number of subjects:
    - i. Initially contacted
    - ii. Initial interviewed

- iii. Consented
- iv. Baseline data collected
- e. Reasons for non-participation:
  - i. After initial contact and/or initial interview
  - ii. After consent process
  - iii. After initial data collection or throughout the study
  - iv. Until end of study
- f. Reasons for participating in and completing study

2) Randomization:

- a. Testing effect of randomization process on distribution of demographic, co-morbidity, and other background characteristics
- c. Testing randomization process on their baseline main outcomes
- d. Examining acceptability of the randomization process and its effect

3) Missing data:

- a. Differences in rates of missing data between medication and placebo groups and per time point
- b. Pattern of missing data

4) Retention rate:

- a. Differences in retention between medication and placebo groups
- b. Factors influencing these differences

5) Subjects' satisfaction with:

- a. Study procedures
- b. Study implementation and staffing
- c. Medication delivery methods
- d. Data collection timepoints and outcomes

6) Medication fidelity with:

- a. Delivery methods
- b. Number of successful and failed deliveries
- c. Assessment methods
- d. Timing and method of feedback

7) Study improvement procedures/maintaining documentation of:

- a. Study/protocol development, revision, and modification
- b. Issues and concerns with implementing recruitment strategies
- c. Issues and concerns with accessing, distributing, and tracking of medication and placebo
- d. Issues and concerns with measurements:
  - i. Number of measurements
  - ii. Time requirements of measurements
  - iii. Redundancy among measurements
  - iv. Positive or negative carryover

Sub-study 1b: mQFPD vs. placebo in acute COVID-19 patients.

The primary objectives of this study are:

- Ascertainment of safety of FoTv and
- Assessment of feasibility of the intervention (with the primary outcomes focusing on determination of the rates of recruitment and completion)

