Each participant will receive a paper copy and an emailed study daily diary requesting this information (temperature readings, blood pressure and/or glucometer readings) as well as symptom scores, and medication compliance. This survey (daily diary) will be generated directly through the study database and will interface directly with the secured study database. Participants who are unable to respond to emails will be allowed to record data into the provided paper diary and report the information at the completion of the study to a member of the study team by phone or photo at intervals specified below. Once this information has been reported, there will be no need for the study team to collect the diary.

Any adverse events, as well as any escalation of care, including urgent care, emergency room, or hospitalization, will be reported to the study team after appropriate medical care has been received, via a dedicated phone number or email address that is specific for urgent matters. A dedicated phone number will be available throughout the entire study period to call a physician member of the study team who is available 24 hours a day, 7 days per week, for urgent matters. Non-urgent messages will be routed to a dedicated email address or study coordinator.

If a study participant is hospitalized as a result of COVID-19, the participant will be instructed to discontinue study medication and the study team will follow up with either the patient or the emergency contact at the end of the trial period, or following the hospitalization, to determine final outcome and obtain laboratory records from the hospitalization.

At Day 14, a telephone call will be conducted among participants who have not been hospitalized to assess for COVID-19 symptoms, review any adverse events, review concomitant medications, drug accountability (participants will take pictures of

their empty bottles and send to the study team), and harmonize any data discrepancy between their daily diary and the study database. At this time, they will have completed the investigational product.

At the time of the Day 14 telephone call, participants who have not been hospitalized will be directed to obtain end-of-trial blood draw via outpatient laboratory or in-home phlebotomy.

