### 6. Adverse Events

- Adverse events are being monitored in three formats: daily communication with study team to report symptoms and adverse event reporting as described elsewhere (see section 15), labs at the end of the 14-day treatment period, and urgent reporting of adverse events via a 24 hour physician staffed phone line (see below). The study team will have a daily communication with subjects where our study coordinators will review all subjects' symptoms and their severity. This information will be tallied daily and will be reported to each site's PI and study main PI and medical monitor. Furthermore, they will be reported to the study DSMB and IRB.
- Information regarding occurrence of adverse events will be captured on the IRB approved standard case report form (CRF) as follows: Duration (start and stop dates and times), severity/grade, outcome, and relation to study medication).

- Any deterioration in cardiac or pulmonary status will be immediately escalated to proper medical attention and that any study participant who is hospitalized for any reason will be required to stop study medication irrespective of the cause of this adverse event. These events will subsequently be reported to the DSMB and IRB for review.
- A list of anticipated side effects of FoTv or mQFPD will be available to study coordinators, as will a list of known symptoms of COVID-19. Any reported symptom on the COVID-19 list will be referred to the study participant's primary care provider.

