### **Statistical Methods And Considerations**

For all sub-studies (1a, 1b, and 1c), data management and statistical analysis will be performed by the Krupp Biostatistical and Data Management Core and will employ the Krupp Data System (KDS). A computer-generated randomization list will be prepared by the study biostatistician and will be used to randomize subjects into one of the two treatment groups with equal probability. For sub-study 1c only, equal number of subjects based on age (18-55 and  $>55$ ) and BMI ( $<30$  and  $\geq 30$ ) will be randomized to the treatment groups. For all sub-studies, randomization tables will be prepared at the beginning of the study and will be maintained by the study biostatistician.

Within each of the sub-studies, the comparability of the two treatment groups in terms of baseline demographic and clinical features will be tested with analyses of variance (ANOVAs) for continuous variables and Chi-square analyses for dichotomous variables. Descriptive statistics and exploratory graphing will be used to assess the distribution, normality, and homogeneity of the data. If needed and applicable, the continuous outcome data will be transformed using an appropriate transformation such as a log transformation. Missing data will be examined to assess randomness and informativeness using methods developed by Diggle (1989). Similarly, we will test whether dropout is random or systematic by comparing the dropouts with the study completers in terms of the baseline data. An absence of significant differences would support the random nature of dropout.

The primary aims of our data analytic strategy will be directed toward assessing the safety of the interventions, antibody titers, vaccine side effects, adherence to treatment, and retention rate. This will help to provide guidance to inform any

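### Sub-studies 1a and 1b: no rule for symptom scores after hospital admission, so the complete-data rank test leans toward no difference if the product worsens COVID-19

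*Combined protocol and SAP*

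**What the plan says.** **Data collection after admission.** Section 9, Sub-studies 1a and 1b, sets the call: "At Day 14, a telephone call will be conducted among participants who have not been hospitalized to assess for COVID-19 symptoms". A participant admitted for COVID-19 stops study medication, and the team later obtains the final outcome and hospital laboratory records. Item 6, Adverse Events, widens the stopping rule: "any study participant who is hospitalized for any reason will be required to stop study medication irrespective of the cause of this adverse event". Under Clinical Laboratory Measurements, End-of-Treatment, hospital results stand in for the Day 14 tests. No text supplies a symptom score in the same way. The Day 28 call includes hospitalized participants, and emergency contacts or hospital records may supply answers.

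**Daily contact.** Item 6 also says "The study team will have a daily communication with subjects where our study coordinators will review" symptoms and their severity. Neither that item nor item 4, Symptoms, says whether contact or diaries continue in hospital.

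**Analysis.** Statistical Methods and Considerations applies a rank-sum test across visits and sites, and explains its backup: "Since nonparametric tests are based on complete data and ignore missing follow-up data, general linear mixed regression modeling" is to confirm the result, "with an assumption that the data is missing at random". For dropout, baseline data are compared between dropouts and completers: "An absence of significant differences would support the random nature of dropout". A separate check of whether missing data are informative is also planned. Adverse events are tabulated by arm, with chi-square tests for dichotomous safety data. Section 6, B. Feasibility, adds a comparison of arms: "Differences in rates of missing data between medication and placebo groups and per time point". The stated use of the measures includes "Determining the primary outcome measure for the main trial by assessing and comparing sensitivity to change of the measures and other statistical properties".

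**The concern.** Admission can be a consequence of the outcome being measured. If a product worsens COVID-19, more of its sickest participants are admitted. If their scores then stop, the rank test compares those who stayed well enough to remain at home, and the arms look more alike than they are.

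Two uses of the scores are at stake. First, Section 14 reports the FDA's concern that FoTv might accelerate or worsen COVID-19, and the sponsor answers that it relies on this Phase 1 study to detect such effects. A null symptom result in 1a could be read as reassurance on that question. The FDA concern is about FoTv, so for mQFPD in 1b only the general point applies. Second, the scores help choose the Phase 2 primary outcome and give effect-size estimates. Leaving out admitted participants shrinks both the sensitivity to change and the effect size. The plan's caution about pilot effect sizes concerns their standard error, not this bias.

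**Working it through.** **The plan's own figure.** 27 evaluable per arm with a 20% allowance: 27 × 1.2 = 32.4, rounded up to 33 per arm, 66 in total. This reproduces. (27 / 0.8 = 33.75 would give 34.) The plan states no power or admission rate for 1a or 1b.

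**Inputs.** 33 per arm and two-sided 0.05 are from Section 9. Admission rates are assumed. Section 14 gives about 19% for COVID-19 cases in general, but 1a and 1b exclude people whose symptoms already require hospitalization, so 5% is more plausible for placebo. Doubling in the active arm is an assumption.

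**Model.** The Day 14 score is normal with SD 1 and higher is worse. Participants above c = z(1 − p0) are admitted and have no score. The arm shift that produces active-arm rate p1 is δ = z(1 − p0) − z(1 − p1).

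- 19% vs 38%: δ = 0.878 − 0.306 = 0.572.
- 5% vs 10%: δ = 1.645 − 1.282 = 0.363.

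**Chance that the rank test flags harm (simulated)**

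| Admitted, placebo vs active | No scores missing | Complete data | Admitted ranked worst |
|---|---|---|---|
| 19% vs 38% | about 60% | 26% | 58% |
| 5% vs 10% | about 30% | 22% | 30% |

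The last column assumes that everyone admitted is still in hospital at Day 14. With a looser link between severity and score (correlation 0.5 or 0.8) and a shift of 0.5 SD, detection falls from 48–50% to 28% or 24% at 19% vs 35%. At 5% vs 13% it falls to 41% or 35%. With no link there is lost power but no bias.

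**What the rest of the plan recovers.** Daily scores were simulated for days 0 to 14, with worsening building up in the diary, admission on days 3 to 10 and scores missing afterwards (10,000 trials per setting):

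| Admitted | Mixed model | Chi-square on hospitalization | Any of the three as planned | Any, with worst-rank rule |
|---|---|---|---|---|
| 19% vs 38% | 70% | 42% | 82% | 82–84% |
| 10% vs 20% | 54% | 21% | 66% | 66–68% |
| 5% vs 10% | 43% | 12% | 54% | 55–56% |

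The mixed model uses every recorded day, so it can exceed a single-day rank test. Treating its covariance as known favours it. At 19% vs 38% it estimates 0.502 against a true 0.572, and 0.502 / 0.572 = 88%. The comparison of missing-data rates is weaker. With the 20% dropout added, missingness is 1 − 0.81 × 0.80 = 35% vs 1 − 0.62 × 0.80 = 50%, flagged in 27% of trials.

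**Effect size among those not admitted.** The mean below the threshold is μ − φ(c − μ)/Φ(c − μ).

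- Harm, 19% vs 38%. Placebo: −0.271/0.81 = −0.335. Active: 0.572 − 0.381/0.62 = −0.042. The difference is 0.29 instead of 0.57.
- Benefit, 19% vs 9.5%. The true difference is 0.43 and the observed one 0.28, or 0.35 in SDs of the remaining group. A Phase 2 sample size would be inflated by (0.43/0.35)² = 1.5. At 5% vs 2.5% the factor is about 1.2.

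**Precision of the hospitalization comparison.** Exact 95% intervals for the risk difference: 2/33 vs 2/33, about −15 to +15 points; 6/33 vs 6/33, about −20 to +20; 13/33 vs 6/33, −1 to +42.

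**The case against.** The plan admits the rank test's weakness in the quoted sentence and adds a mixed model because of it. No Day 14 symptom comparison is a named endpoint, since 1a and 1b are about safety and feasibility. Hospitalized participants are followed: the team determines their final outcome, the Day 28 call covers them, Section 12 provides hospital data to an endpoint adjudication committee, and Section 16 assigns adjudication of hospital records. Diaries may continue after admission. Effect sizes are said not to be the main focus, and the Phase 2 protocol is still to come. At 27 evaluable per arm, overall detection at 19% vs 38% is 75.4% as planned and 75.2–77.6% with worst ranks, so it could even fall slightly.

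All of this stands, and it sets the weight of the point. None of it supplies a symptom score after admission or says which analysis prevails if the rank test and mixed model disagree.

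A reader might go further and infer that both symptom analyses, and the baseline dropout check, would fail when deterioration is sudden. That can be simulated only by making admission unrelated to earlier scores, in which case no analysis of recorded scores could succeed. The failure is built into the assumption and says nothing about what the plan would do in practice. Where worsening builds up in the diary, comparing baseline scores of admitted and other participants finds a difference in 89% of simulated trials at 19% vs 38%.

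**Conclusion.** The point holds as a low-cost improvement. The gap in the rule is plain from the text. The bias is conditional: it needs scores to stop at admission and admission to track severity. Under those conditions the complete-data rank test loses more than half its chance of flagging harm at 19% vs 38%, and about a quarter (30% to 22%) at 5% vs 10%. The mixed model makes up most of the loss when worsening appears before admission.

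A reader might infer that harm would be hidden from the trial or that a primary result is biased. The documents support neither. Hospitalization is an adverse event, tabulated by arm and open to a chi-square test, and no named endpoint depends on the Day 14 score. Changing the rule raises overall detection by only 0 to 3 points. What improves is the symptom result itself, which would be less likely to reassure wrongly on the FDA's FoTv question, and the figures carried into Phase 2. All admission rates and the link between severity and score are assumptions.

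**What to change.** 1. In Section 9, Sub-studies 1a and 1b, make the Day 14 symptom call to all participants, including those admitted or already discharged. Allow emergency contacts or hospital records to answer, as at Day 28.
2. In Statistical Methods and Considerations, add: any-cause hospitalization or death by Day 28 is compared in all randomized participants, whatever the attributed relationship to treatment, as a risk difference with an exact 95% confidence interval. A non-significant result does not show absence of harm.
3. As a supporting analysis, give the worst rank in the symptom rank test to participants who have died, or who are in hospital with no score at that time point. Use observed scores wherever they exist, and read the result alongside the retained mixed model.

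The cost is a few sentences, a few lines of code and some extra calls: about 6 to 13 per arm at 19–38% admitted (33 × 0.19 = 6.3; 33 × 0.38 = 12.5), and 2 to 3 at 5–10%. No visits or participants are added. A worst-rank test gives no simple mean difference, and its gain shrinks if most of those admitted have gone home recovered by Day 14. The chance of a false harm signal across the three analyses stays similar: 6–7% as planned and 5–7% after the change.
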